11 DOSING OF STUDY DRUG

11.1 General Dosing Information

Gaseous NO (5000 ppm), delivered with air as carrier to dilute it to 160 ppm, will be administered by inhalation for 50 minutes three times daily on Days 1-5, 8-12, and 15-19. On each day, treatment will be given with a minimum of 3 hours between the end of one treatment and the start of the following treatment. Subjects will receive 160 ppm during each 50 minute inhalation period (daily exposure 400 ppm hours). This will result in a total of 6000 ppm hours of exposure.

11.2 Dosing Information

The 5000 ppm nitric oxide source cylinder contains 5000 ppm (0.5% NO) with the balance of the gas being nitrogen. Only 3.2% of the gas the subject inhales will come from the NO cylinder. Therefore, the nitrogen in the NO cylinder will dilute the inspired oxygen in the carrier gas. This will lower the inspired oxygen from 20.9% to 20.3% or the equivalent of standing at approximately 700 feet above sea level. Inclusion criteria for subjects include oxygen saturation >90% on room air and the estimated 3.5 torr change in PaO₂ is not anticipated to have a significant clinical effect on subject oxygenation. Subjects will be monitored continuously during treatment with a pulse oximeter.

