10.2 Exclusion Criteria

Subjects will be excluded if they have any of the following:

- Smoking history in the prior 6 months
- Significant hemoptysis within 30 days prior to screening (>5 ml of blood in one coughing episode or >30 ml of blood in a 24 hour period)
- Forced expiratory volume at one second (FEV₁) <40% of predicted
- On supplemental oxygen or SaO₂ <90% at screening or Day 1, or within 30 days prior to enrollment.
- Known cardiac (left heart) insufficiency (defined as LVEF <35%) prior to screening
- Known pulmonary hypertension
- Known or suspected hemoglobinopathy
- Initiation of NTM treatment regimen or a change in the regimen was made in the prior 6 months. Subjects on active treatment can be enrolled if they have been on a stable anti-NTM regimen for at least 6 months.
- Initiation of new chronic therapy within 4 weeks prior to screening
- Use of drugs known to increase methemoglobin (see 12.2.7) at screening
- Any of the following abnormal lab values at screening:
 - 6-GPD deficiency
 - Hemoglobin <10g/dl
 - Platelet count <100,000/mm³
 - Prothrombin time international ratio (INR) >1.5
 - Abnormal liver function defined as any two of the following
 - ALT >3x ULN
 - AST >3x ULN
 - ALP >3x ULN
 - GGT >3x ULN
 - Abnormal renal function defined as:
 - Calculated Creatinine Clearance <50 ml (as calculated by Cockcroft/Gault)
- For women of child bearing potential:
 - Positive pregnancy test at screening or
 - Lactating or
 - Unwilling to practice a medically acceptable form of contraception from screening to Day 15 (acceptable forms of contraception: abstinence, hormonal birth control, intrauterine device, or barrier method plus a spermicidal agent)
- Use of an investigational drug within 30 days prior to screening
- Intravenous or oral steroids (>10 mg/d prednisone equivalent) in the 14 days prior to screening
- Any condition that the Investigator believes would interfere with the intent of this study or would make participation not in the best interest of the subject.

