12.2.4 Oxygen Saturation

Oxygen saturation will be measured by pulse oximetry on room air at multiple visits during the study after the subject has been at rest for 5 minutes. Additionally, during each 50 minute inhalation treatment period, measurements will be recorded at 0, 5, 10, 15, 20, 25, 30, 35, 40 and 45 minutes.

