13 DISCONTINUATION OR WITHDRAWAL FROM TREATMENT

13.1 Discontinuation of a 50 Minute Inhalation Period (note: treatment will not be initiated if threshold values are present beforehand)

A 50 minute inhalation treatment period will be discontinued if the following occurs.

- a change in the blood pressure systolic value ≥ 20 mmHg or an absolute value of ≤ 80 mmHg repeated at 2 minutes
- an oxygen saturation of $< 85\%$ and following recheck of sensor placement
- a reduction in oxygen saturation $> 5\%$ (e.g. 98% to 92%).
- a persistent* increase in heart rate of ≥ 30 from start of a treatment or an absolute value of 150
- a persistent* absolute increase in methemoglobin of more than 5% above the Day 1 baseline value and following recheck of sensor placement
- a recorded inspired NO₂ > 5 ppm during any treatment
- Subjects with methemoglobin of more than 15% should be treated with 100% oxygen. If 20% or greater, subjects should be treated with Methylene Blue (1 to 2 mg/kg intravenously). Repeat in one hour if necessary. Note: Inject intravenously very slowly over a period of several minutes to prevent local high concentration of the compound from producing additional methemoglobin. Large intravenous doses of Methylene Blue may produce nausea, abdominal and precordial pain, dizziness, headache, profuse sweating, mental confusion and the formation of methemoglobin. Also note that methemoglobin cannot be measured by the oximeter after treatment with methylene blue and should be measured by blood values. See package insert for full contraindications and side-effects. Methylene blue is contraindicated in patients who have developed hypersensitivity reactions to it and in severe renal insufficiency. It is relatively contraindicated in G6PD deficient patients as it can cause severe hemolysis and also in patients with Heinz body anemia. In such cases it may be appropriate to treat with intravenous ascorbic acid.

*Persistent means that the value was obtained on a repeated measurement taken 5 minutes following the original measurement.

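### In the visible text, an inhalation after Day 1 can start at a saturation of 85–89%, below the entry level that section 11.2 partly relies on

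*Combined protocol and SAP*

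**What the plan says.** **Premise.** Section 11.2 explains that cylinder nitrogen lowers inspired oxygen from 20.9% to 20.3%. It judges this clinically unimportant on three supports: a small estimated PaO2 change (3.5 torr), continuous oximetry, and the statement that "Inclusion criteria for subjects include oxygen saturation >90% on room air".

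**Entry rule.** Section 10.1 contains no saturation criterion. Section 10.2 excludes subjects on supplemental oxygen or with SaO2 "<90% at screening or Day 1, or within 30 days prior to enrollment". It names no later day.

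**Rule before each inhalation.** Table 12.1 requires an SaO2 reading before treatment but gives no cut-off. Section 12.2.4 says "Oxygen saturation will be measured by pulse oximetry on room air at multiple visits". The heading of 13.1 adds "note: treatment will not be initiated if threshold values are present beforehand". The saturation thresholds listed there are a value below 85%, after the sensor is rechecked, and "a reduction in oxygen saturation" of more than 5%, with 98% to 92% as the example.

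**References in the same list.** Heart rate is judged "from start of a treatment or an absolute value of 150". Methemoglobin is judged by an "absolute increase in methemoglobin of more than 5% above the Day 1 baseline value". The blood pressure item, "a change in the blood pressure systolic value", names no reference, and neither does the saturation fall.

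**Consequence of stops.** Under 13.2, a subject who has had to stop an inhalation more than twice on 13.1 criteria is withdrawn.

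**The concern.** Part of the argument for the diluted gas is a saturation level that is checked at entry and not required again. Dosing continues for 14 more treatment days in people with chronic lung disease, and saturation can drift. A subject whom 10.2 would have excluded on Day 1 can be dosed on Day 2 at the same reading.

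Two things are at stake. The first is safety: the inhalation may begin outside the condition stated in 11.2 and, at the low end, beside the limit that stops it. The second is completeness: repeated stops lead to withdrawal in a study of 6 to 10 subjects. In addition, two sites could apply a fall with no stated reference in different ways.

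**Working it through.** **1. The plan's own figures.**
- Cylinder share (11.2): 160/5000 = 3.2%, as stated.
- Inspired oxygen: 20.9 × (1 − 0.032) = 20.23%, against a stated 20.3%. The difference is under 0.1 point, and the change is small either way.
- The 3.5 torr figure cannot be reproduced because its inputs are not given. Nothing below depends on it.
- Exposure (11.1): 160 × 50/60 = 133.3 ppm-hours per inhalation; × 3 = 400 per day; × 15 days = 6000. All agree.

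**2. Inhalations after the last day with a 90% rule.** 3 × 15 = 45 planned; 45 − 3 on Day 1 = 42. This counts occasions, not events.

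**3. Lowest permitted start.** Take integer readings. Let B be the Day 1 value (at least 90 by 10.2) and R the reading before a later inhalation. Every reading of 13.1 requires R ≥ 85. The fall criterion then adds one of the following:
- Reference Day 1, in points: B − R ≤ 5.
- Reference Day 1, relative: R ≥ 0.95 × B, which is 85.5, 86.45, 87.4, 88.35 and 89.3 for B = 90 to 94.
- Reference the start of the same treatment: nothing, since no fall can have occurred yet.

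Permitted starts below 90%:

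| Day 1 value (%) | Day 1, points | Day 1, relative | Start of treatment |
|---|---|---|---|
| 90 | 85–89 | 86–89 | 85–89 |
| 91 | 86–89 | 87–89 | 85–89 |
| 92 | 87–89 | 88–89 | 85–89 |
| 93 | 88–89 | 89 | 85–89 |
| 94 | 89 | none | 85–89 |
| 95 or more | none | none | 85–89 |

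Each of the three readings permits some start below 90%. The plan's example favours points: from 98%, 92% is the first integer more than 5 points down, whereas on a relative reading 93% would already qualify (5/98 = 5.1%). The example does not say from when the fall is measured.

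**4. Start limit against stop limit.** A start is allowed at 85% and an inhalation stops below 85%, so at the lowest permitted start a one-point drop to 84% stops it. A third such stop means withdrawal. One subject is 1/10 = 10% to 1/6 = 17% of the sample.

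**The case against.** **A pre-dose rule already exists.** This stands. A reader might infer that saturation is not checked before dosing after Day 1. The documents do not support that: Table 12.1 requires the reading and 13.1 bars a start at its thresholds. Entry criteria also need not equal dose-hold limits. What remains is that the hold limit is the same number as the in-treatment stop, and lies below the level cited in 11.2.

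**11.2 does not rest on 90% alone.** This also stands. It relies as well on the small dilution and on continuous oximetry, and it does not say that saturation must exceed 90% before every inhalation. A reader might infer that the case for the gas collapses without the 90% level, or that starting at 85–89% is shown to be unsafe. The documents show neither.

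**The any-subject reading leaves the pre-start note idle for the fall criterion.** This is a fair reason to prefer Day 1, but not a decisive one. The heart-rate rise is expressly measured from the start of a treatment, so the note is idle for that criterion too.

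**Other safeguards.** Section 15.1.6 lists acute hypoxia as an adverse event of special interest. The delivery device in 11.3 monitors inspired oxygen. The Medical Monitor may pause the study, and the investigator may withdraw a subject. Section 6 reports that saturation stayed at 95% or above in eight adults with cystic fibrosis at 160 ppm, with 30-minute rather than 50-minute inhalations. These lower the concern. None sets a saturation floor before dosing, and the earlier result does not describe subjects whose baseline is near 90%.

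**Section 11.3 breaks off mid-sentence in the available text.** A start rule could sit there, so the point is limited to what is visible.

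**Conclusion.** The point holds as a gap in a safety rule, of low to moderate severity. In the visible text, inhalations after Day 1 may start at 85–89%. For any subject to be exposed to this, the fall must be measured from the start of that treatment. With a Day 1 reference it is confined to Day 1 values of 90–94% (points) or 90–93% (relative), and nobody at 95% or above is affected.

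The conclusion assumes integer oximeter readings and that no rule appears in the missing part of 11.3. The number of subjects affected cannot be estimated, because the documents give no baseline saturations for the study population. The mismatch between an inclusion of >90% in 11.2 and an exclusion of <90% in 10.2 matters only at exactly 90% and is editorial. Neither the sample size nor the efficacy analysis is directly affected.

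**What to change.** First check the full text of 11.3. If it contains no start rule:

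- **13.1 and Table 12.1:** require SaO2 of at least 90% on room air before each inhalation. If it is lower, recheck the sensor and repeat after 5 minutes. If it is still below 90%, hold that inhalation and record it as missed, not as a discontinuation counting toward 13.2. Keep <85% as the stop limit during treatment.
- **References for the fall:** state that a fall of more than 5 points is judged against the Day 1 value before dosing and against that inhalation's pre-dose value during dosing.
- **11.2:** cite the 10.2 exclusion and the new start rule in place of an inclusion criterion.

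The split reference matters. With the pre-dose value as the only reference, a subject at 98% on Day 1 could start at 92%, which a Day 1 reading of the current text blocks. Under the fix a start needs R ≥ max(90, B − 5), so no start now blocked on the Day 1 points reading or the start-of-treatment reading is released. Only if a relative fall was meant would it free a single value, B − 5, for B = 95 to 99 (for example 93% from 98%, since 0.95 × 98 = 93.1).

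**Cost.** This is an amendment using a reading already taken. Each held inhalation loses 133.3/6000 = 2.2% of planned exposure, or 400/6000 = 6.7% for a whole day, mainly in subjects with a baseline near 90%. If the sponsor meant the start of treatment, some starts at or above 90% would also be newly held: 90% for a Day 1 value of 96%, up to 90–94% for 100%. If Day 1 was also meant during dosing, the in-treatment stop becomes less strict. For example, with Day 1 at 98% and a pre-dose value of 93%, a reading of 92% is 6 points below Day 1 but only 1 below pre-dose. The sponsor should confirm that this is acceptable.

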11.3 Dosage Administration

Gas cylinders with the study drug (5,000 ppm NO and 99.5% nitrogen) will be labeled with its contents. These cylinders will be D-size cylinders with a CGA626 valve, containing approximately 350 liters of gas.

Subjects will receive the study drug by inhaling through a nasal mask attached to an Inhaled NO Delivery Device (INODD) administration system. The INODD is comprised of three components including an inspiratory flow monitor with a ratio-metric matching NO injector module, an inhaled gas monitoring module, and a gas mixing subject interface and breathing valve. It is a variable inspiratory flow delivery system that instantaneously matches the subject's inspiratory flow with the injected 5000 ppm NO to deliver 160 ppm of nitric oxide independent of inspiratory flow up to 120 LPM, while keeping nitrogen dioxide \leq 3 ppm. It is a breath-initiated delivery system and the NO will be blended into the inspiratory gas stream only as long as the subject is inhaling and proportional to the inspiratory flow. The analyzer monitors the inhaled nitric oxide, nitrogen dioxide and oxygen concentrations.

A sample pump in the INODD withdraws a low flow (~ 250 mL/min) from the inspiratory circuit to the subject for analysis of NO, NO₂ and O₂. These analyzers assure that the subject is receiving the correct gas concentration and assures that the oxygen concentration remains in a safe range and that the inspired concentration of NO₂ is below the set alarm threshold limit. Should the NO concentration fall outside the targeted range, an operator set alarm will sound. The system will shut off the NO flow should the NO analyzer measure a value that is \geq 200 ppm. In addition, should the NO₂ rise above the alarm limit of 3 ppm, an alarm will sound. If the NO₂ rises above 5 ppm, the system will alarm as well as shut off the flow of NO to the

12 ASSESSMENTS

12.1 Timing of Assessments

The timing of assessments is shown in Table 3-1.

12.2 Clinical Assessments

12.2.1 Subject and Disease Characteristics

Demographic information (age, gender, race) will be captured at Screening. Relevant medical history, including history of current disease, other pertinent respiratory history, and information regarding underlying diseases will be recorded at Screening.

12.2.2 Physical Examination

A complete physical examination will be performed by a physician (either the principal investigator or a sub-investigator) at Screening. Body systems to be examined include General, Skin, Lymph Nodes, HEENT, Respiratory, Cardiovascular, Gastrointestinal, Neurologic and Musculoskeletal. Qualified staff (e.g. MD, nurse practitioner, registered nurse, physician's assistant) may complete the abbreviated physical exam (General, HEENT, Respiratory, Cardiovascular and Gastrointestinal) at all other visits. After screening, new clinically significant abnormal physical exam findings must be documented as adverse events (AEs) and will be followed by a physician or other qualified staff at the next scheduled visit or as medically indicated.

12.2.3 Vital Signs

Heart rate, blood pressure, respiration rate and temperature will be performed and recorded after resting for 5 minutes at Screening and prior to the start of the first treatment on each day of treatment. Heart rate from the pulse oximeter will additionally be measured and recorded every 5 minutes during each treatment.

12.2.4 Oxygen Saturation

Oxygen saturation will be measured by pulse oximetry on room air at multiple visits during the study after the subject has been at rest for 5 minutes. Additionally, during each 50 minute inhalation treatment period, measurements will be recorded at 0, 5, 10, 15, 20, 25, 30, 35, 40 and 45 minutes.

12.2.5 Methemoglobin

Will be non-invasively measured (and recorded every 5 minutes) using a pulse methemoglobinometer at Screening, Baseline, continuously during each treatment, recorded every 5 minutes during each treatment. For the first treatment, subjects will be monitored in clinic every 30 minutes post-treatment for adverse events related to study drug inhalation and to

ensure MetHb returns to baseline. NOTE: Any Methemoglobin level >5% (absolute) above baseline requires a repeat level to be measured 5 minutes later and the final measurement should be recorded. If methemoglobin is 15% or higher, see section 13.1 for treatment procedures.

Table 12.1 Monitoring before, during and after treatment

Measurement	Pre-treatment	During treatment	Post-treatment
Vital signs	HR, BP, RR, T prior to first treatment HR, BP, RR prior to each treatment	HR every 5 minutes	HR, BP, RR upon cessation of treatment Repeat at 30 minutes
SaO2	Prior to treatment	Every 5 minutes	Upon cessation of treatment Repeat at 30 minutes
Methemoglobin	Prior to treatment	Every 5 minutes	Upon cessation of treatment Repeat every 30 minutes until return to baseline

12.2.6 Prior and Concomitant Medications

Information regarding all medications administered before study enrollment and through the last study visit will be recorded.

12.2.7 Excluded concomitant medications

Some medications are known to be capable of inducing methemoglobinemia and are excluded from use in this trial. This list may include:

Chart I – Drugs Capable of Inducing Methemoglobinemia

- Acetaminophen	- Anti malaria drugs	- Nitrates	- Nitric oxide
- p-Aminosalicylic acid	- Chloroquine	- Ammonium nitrate	- Nitrous oxide
- Local anesthetics	- Primaquine	- Silver nitrate	- Piperazine
- Benzocaine	- Quinacrine	- Sodium nitrate	- Rifampin
- Bupivacaine	- Methylene blue	- Nitroglycerine	- Riluzole
- Lidocaine	- Dapsone	- Nitroprusside	- Sulfonamides
- Prilocaine	- Phenacetins	- Bismuth subnitrate	- Sulfasalazine
- EMLA*	- Phenazopyridine	- Nitrates	- Sulfamethoxazole
- Anticonvulsants	- Flutamide	- Amyl nitrate	- Sulfadiazine
- Valproic acid	- Hydroxylamine	- Isobutyl nitrate	- Sulfapyridine
- Phenytoin	- Oral hypoglycemics	- Nitrofurantoin	- Sulfanilamide
	- Metochlopramide		- Sulfones

*Eutetic mixture of local anesthetics.

12.3**Safety**

Study subjects will remain in the research clinic for at least one hour following each treatment, presuming all monitored parameters are acceptable as per Table 12.1

12.3.1**Adverse Events**

Information regarding occurrence of adverse events will be captured throughout the study. Duration (start and stop dates and times), severity, outcome, treatment and relation to study medication will be documented on the case report form.

12.3.2**Safety Monitoring**

A Medical Monitor for this study will consist of a single independent monitoring clinician with experience in the treatment and management of patients with pulmonary diseases. Safety data will be monitored on a continual basis throughout the trial. SAEs and important protocol defined medical events will be reviewed in real time throughout the trial. The Medical Monitor will review all SAE reports and important protocol defined medical event reports, and may at any point temporarily stop the study for concerns of subject safety. IND safety reporting to the FDA and the IRB will be according to guidance procedures as delineated in CFR 312.32.

12.4**Research Laboratory Assessments****12.4.1****Sputum cultures**

Sputum will be collected for culture at Screening, and Days 5, 12, and 19 (treatment dates), and Weeks 7, 11 and 15 (follow up). Sputum samples will be processed at the MUSC clinical laboratory, using standard decontamination procedures, fluorochrome microscopy, solid medium culture on a biplate of Middlebrook 7H10 agar with and without antibiotics, and a broth culture (BACTEC 960 [Becton Dickinson, Sparks, MD] or ESP [TREK Diagnostic Systems, Cleveland, OH]). MAC isolates are identified with AccuProbe (Hologic-GenProbe, San Diego, CA).

Semiquantitative AFB smear and culture results for each submitted clinical specimen will be recorded [Wallace 1996]. Briefly, a negative culture exhibits no mycobacterial growth. Cultures will be reported as positive if growth occurs in broth medium only; growth on broth medium plus solid medium cultures with countable colonies will be reported as 0–49 colonies, 1+; solid medium growth with 50–99 colonies, 2+; solid medium growth with 100–199 colonies; 3+, solid medium growth with 200–299 colonies; and 4+, solid medium growth with at least 300 colonies. For data analysis, each culture will be scored as follows: 0, no growth in broth or solid medium; 1, broth medium growth only; 2, countable colonies (<50 colonies) on solid medium; and 3–6, 1+ to 4+ growth on solid medium, respectively.

12.5.1**Quality of life measures**

Validated instruments will be used for measurement of symptoms and quality of life. Since study subjects may have different underlying conditions, for which there are different quality of life measures, we will use a condition specific measure for each as follows:

NO-NTM

- Cystic fibrosis: Cystic fibrosis Questionnaire-Revised (CFQ-R)
- Bronchiectasis: Quality of Life – Bronchiectasis (QOL-B)
- All: St. George's Respiratory Questionnaire (SGR-Q)
- All: Leicester Cough Score

13 DISCONTINUATION OR WITHDRAWAL FROM TREATMENT

13.1 Discontinuation of a 50 Minute Inhalation Period (note: treatment will not be initiated if threshold values are present beforehand)

A 50 minute inhalation treatment period will be discontinued if the following occurs.

- a change in the blood pressure systolic value ≥ 20 mmHg or an absolute value of ≤ 80 mmHg repeated at 2 minutes
- an oxygen saturation of $< 85\%$ and following recheck of sensor placement
- a reduction in oxygen saturation $> 5\%$ (e.g. 98% to 92%).
- a persistent* increase in heart rate of ≥ 30 from start of a treatment or an absolute value of 150
- a persistent* absolute increase in methemoglobin of more than 5% above the Day 1 baseline value and following recheck of sensor placement
- a recorded inspired NO₂ > 5 ppm during any treatment
- Subjects with methemoglobin of more than 15% should be treated with 100% oxygen. If 20% or greater, subjects should be treated with Methylene Blue (1 to 2 mg/kg intravenously). Repeat in one hour if necessary. Note: Inject intravenously very slowly over a period of several minutes to prevent local high concentration of the compound from producing additional methemoglobin. Large intravenous doses of Methylene Blue may produce nausea, abdominal and precordial pain, dizziness, headache, profuse sweating, mental confusion and the formation of methemoglobin. Also note that methemoglobin cannot be measured by the oximeter after treatment with methylene blue and should be measured by blood values. See package insert for full contraindications and side-effects. Methylene blue is contraindicated in patients who have developed hypersensitivity reactions to it and in severe renal insufficiency. It is relatively contraindicated in G6PD deficient patients as it can cause severe hemolysis and also in patients with Heinz body anemia. In such cases it may be appropriate to treat with intravenous ascorbic acid.

*Persistent means that the value was obtained on a repeated measurement taken 5 minutes following the original measurement.

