9.1.2 Treatment Period (Days 1-15)

The treatment period is separated over 3 weeks (A, B, and C) each with 5 days of treatment, and 2 days off treatment in between. On the first day of each treatment week (A1, B1, C1) subjects will be evaluated for any changes in health or medications. They will undergo physical examination, including height and weight. They will undergo measurement of efficacy outcomes (symptom scores) as per the Study Assessment Schedule (Table 3-1). During each day of treatment (A1-A5, B1-B5, and C1-C5), subjects will be exposed to gNO through a tight-fitting mask at 160 ppm for 50 minutes for each treatment. There will be three treatments given on each day, with 3 hours between each treatment. The subjects will be monitored with pulse oximetry throughout their exposure to gNO to assess SaO₂ and metHb levels. On the last day of each treatment period (A5, B5, C5), the subjects will repeat their symptom scores as well as provide sputum for mycobacterial culture.

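### Section 13.1 stops a running inhalation on systolic blood pressure, but no blood pressure reading is scheduled during any inhalation

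*Combined protocol and SAP*

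**What the plan says.** Section 13.1 lists conditions under which an inhalation is to be discontinued. The first is "a change in the blood pressure systolic value" of at least 20 mmHg, or an absolute value of 80 mmHg or below, repeated at 2 minutes. A note in the section heading adds that treatment is not started if a threshold is already met.

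Table 12.1 sets the monitoring around each inhalation. For vital signs:

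- Before: "HR, BP, RR prior to each treatment".
- During: "HR every 5 minutes".
- After: "HR, BP, RR upon cessation of treatment", with a repeat at 30 minutes.

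Section 12.2.3 places blood pressure at screening and before the first treatment of each day. Its only in-treatment item is this: "Heart rate from the pulse oximeter will additionally be measured and recorded every 5 minutes during each treatment". Section 9.1.2 says subjects are "monitored with pulse oximetry throughout their exposure to gNO", and section 11.2 likewise mentions only the pulse oximeter. Table 3-1 shows vital signs by visit day, with no timing within an inhalation.

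**The concern.** A rule that interrupts an exposure needs a reading taken during that exposure. Followed exactly as written, the plan gives the blood pressure rule nothing to act on until the inhalation is over. A subject could cross the protocol's own safety threshold and keep inhaling 160 ppm to the end, unless someone takes an unscheduled reading.

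The rule is also incomplete. Section 13.1 gives no direction for the systolic change and does not say which reading it is measured from. Heart rate is referred to the start of the treatment and methemoglobin to the Day 1 baseline. The oxygen saturation reduction names no reference either. For both, the natural reading is the pre-treatment value of the same inhalation.

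**Working it through.** **1. Each section 13.1 stopping parameter against its in-treatment measurement**

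| Parameter | Measured during the inhalation? | Where |
|---|---|---|
| Systolic blood pressure | No | Table 12.1 and 12.2.3: before and after only |
| Oxygen saturation | Yes: "measurements will be recorded at 0, 5, 10, 15, 20, 25, 30, 35, 40 and 45 minutes" | 12.2.4, Table 12.1 |
| Heart rate | Yes, every 5 minutes | 12.2.3, Table 12.1 |
| Methemoglobin | Yes: "continuously during each treatment, recorded every 5 minutes during each treatment" | 12.2.5, Table 12.1 |
| Inspired NO₂ | Yes, by the device analyzer | 11.3 |

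Four of five have a measurement. Blood pressure is named in the Table 12.1 cells on either side of the gap, and section 12.2.3 independently leaves it out, so a damaged table is an unlikely explanation. The 2-minute repeat in section 13.1 confirms a first abnormal reading; it does not schedule that first reading.

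**2. Number of inhalations (section 11.1)**

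3 per day × 15 treatment days = 45 per subject, with 45 × 0 = 0 scheduled in-treatment blood pressure readings.

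**3. Exposure past the threshold**

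The plan's own figures reproduce: 3 × 50 min = 2.5 h, and 2.5 × 160 = 400 ppm-hours per day; × 15 days = 6000 ppm-hours. One inhalation is 160 × 50/60 = 133 ppm-hours.

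- As planned, a change at the very start is seen at cessation: at most 50 minutes, or 133 ppm-hours.
- With readings every 10 minutes plus the repeat: at most 12 minutes, 160 × 12/60 = 32 ppm-hours.
- With readings every 15 minutes plus the repeat: at most 17 minutes, 160 × 17/60 = 45 ppm-hours.

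**4. Extra readings**

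At 15, 30 and 45 minutes: 3 per inhalation, 3 × 45 = 135 per subject. At 10, 20, 30 and 40 minutes: 4 per inhalation, 4 × 45 = 180 per subject.

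**5. Possible effect on withdrawals**

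Section 13.2 withdraws a subject after more than two section 13.1 stops, that is, at the third. The documents give no rate of blood pressure stops, so p below is an assumed proportion of inhalations with a confirmed stop. With inhalations taken as independent, P(X ≥ 3) = 1 − Σ C(45,k) pᵏ(1−p)⁴⁵⁻ᵏ for k = 0, 1, 2. Expected withdrawals are n × P, for the planned range of 6 to 10 subjects (section 14.1).

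| p | P(at least 3 stops) | Expected at n = 10 | Expected at n = 6 |
|---|---|---|---|
| 1% | 0.0104 | 0.10 | 0.06 |
| 2% | 0.0610 | 0.61 | 0.37 |
| 5% | 0.3923 | 3.92 | 2.35 |

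**The case against.** The gap is narrower than a bare reading suggests. Staff see heart rate, saturation and methemoglobin every 5 minutes, and a schedule is a minimum that does not forbid a cuff reading when something looks wrong. The blood pressure threshold is not idle: the pre-treatment reading can bar the next inhalation, readings follow at cessation and 30 minutes later, and subjects stay in the clinic for at least an hour (section 12.3). Blood pressure is not among the adverse events of special interest. The phase I study described in the introduction, at the same concentration but with 30-minute inhalations, reported nothing serious attributed to the drug. The 133 ppm-hours is the planned dose of one inhalation, not an overdose. The withdrawal figures rest on assumed rates and on independence that is doubtful within a subject, and they leave out stops for other reasons, which count toward the same limit.

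Most of this stands as a limit on the size of the problem. What remains is a change without symptoms and without another sign that prompts a check. Section 13.1 does not make its rule conditional on symptoms, and a reading at cessation cannot stop an inhalation that has ended. The case for calling this an inconsistency does not depend on the withdrawal figures, which only illustrate what the fix might cost.

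Two textual caveats apply. The 2-minute repeat could be read as attaching only to the 80 mmHg limb; for the 20 mmHg limb the upper bounds would then be 10 to 15 minutes. Section 11.3 breaks off mid-sentence in the text available here, so the search covers the readable text.

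**Conclusion.** The concern holds. A mandatory safety stop has no scheduled reading to trigger it during exposure: 1 of 5 stopping parameters, in all 45 inhalations per subject. The consequence is possible continued exposure past the protocol's own threshold, for at most 50 minutes per inhalation. How often this would happen cannot be estimated from the documents.

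It is not a counting error. Section 13.2 counts inhalations actually stopped, and an unseen change produces no stop to miscount. The adverse event summaries are not miscounted, and the primary culture endpoint is not directly affected. This should be corrected, but it does not undermine the trial. Confidence is high because the conclusion rests on the text rather than on any assumed rate.

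**What to change.** - **Table 12.1 and section 12.2.3:** add systolic blood pressure during treatment at an interval chosen by the sponsor, for example every 10 to 15 minutes, and keep the 2-minute repeat in section 13.1. In the same edit, bring section 12.2.3 into line with Table 12.1, which already takes blood pressure before every treatment and not only the first of the day.
- **Section 13.1:** say whether the 20 mmHg change means a fall or a change either way, and that it is measured from the pre-treatment reading of the same inhalation. Settle this before the readings begin. State the reference for the saturation reduction in the same way.

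The cost is a short amendment and the 135 to 180 extra cuff readings per subject shown above, using a measurement already made before and after each treatment. The real downside is that more inhalations may be stopped, and a third stop withdraws the subject, possibly before the Day 19 culture; with 6 to 10 subjects that could matter. These are stops the existing rule already requires. If only falls are meant, saying so avoids stops for rises.
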